 5. Delirium
 6. Septic Shock
2. Postoperative ICU admission (yes/no)
3. Prolonged Postoperative Length of Stay (LOS) (greater than vs. less than or equal to CIHI Expected Length of Stay (ELOS) as assigned by the Case Mix Grouping) [note that the LOS includes the day of surgery]
4. Hospital readmission within 30 days (yes/no)
5. Intraoperative mortality (yes/no)
6. Days alive and out of hospital at 30 days postoperatively (28)

III. Other predictors included into model

The following potential perioperative predictors will be evaluated as covariates during model building. Statistically significant predictors will be retained in the model.

Table 2. Other predictors

Preoperative	
 1. Demographics: age on date of surgery, sex, obesity (body mass index>30) 2. Indicators of preoperative comorbidities: since no comorbidity score has perfect performance, a variety of models will be evaluated and the most significant predictive score will be retained in the model. 
 • American Society of Anesthesiologist class • RCRI score(29), and specific components via ICD codes (history of ischemic heart disease, congestive heart failure, cerebrovascular disease, diabetes, chronic kidney disease, and CCI and Case Mix Group codes of suprainguinal vascular, intraperitoneal, or intrathoracic surgery) using previously published methods (30)(31) • Elixhauser comorbidity index (32) and Charlson Comorbidity Index (33): calculated using diagnoses from the previous three years according to standard algorithm by HDNS. Reported as both total score and individual categories • Hospital Frailty Risk Score (34): based on ICD codes • Preoperative blood pressure: ICD diagnosis of hypertension and by measured blood pressure • Preoperative heart rate: Innovian and HSM • Chronic Obstructive Lung Disease (ICD code): since it may affect the interpretation of results of SpO₂ and EtCO₂ 3. Indicators of surgical complexity 
 • CIHI DAD Case Mix Group (CMG) class (also contains categories that include medical complexity) • Main Surgical Service • Procedural Index for Mortality Risk (PIMR) (35): according to CCI • Procedure: CCI codes • Preoperative ICU admission • Emergency surgery: as determined by DAD Method of Entry = emergency department or transferred from another institution)

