CIHI DAD	PATIENT_ID: encrypted health card number For HDNS internal use	Patient	Jan 1, 2013 to Dec 1, 2017	HDNS data linkage with Innovian-HSM. The dataset given to us will not contain Patient_ID, but rather a Study ID.
Vital Statistics	PATIENT_ID: encrypted health card number For HDNS internal use	Patient	Jan 1, 2013 to Dec 1, 2017	HDNS data linkage with Vital Statistics. The dataset given to us will not contain Patient_ID, but rather a Study ID.
CIHI DAD	PDATE[1-n]: procedure date	Patient	Jan 1, 2013 to Dec 1, 2017	HDNS data linkage with Innovian surgery date, to ensure that only the admission corresponding to the surgery admission of interest (first surgery admission with LOS>1) is included.

				
The PDATE matching the date of procedure (+/- 1 day) from Innovian will be used. The corresponding number (e.g. PDATE1) will be used for all procedure-related codes (e.g. PCODE1, PDSERV1).
 
Note that except for preoperative comorbidity data, where we would need data for 3 years prior to PDATE, for all other variables we only need data within 30 days after PDATE.

CIHI DAD	
LOS: Length of Stay (after surgery)
 
Derived by HDNS: discharge date minus PDATE + 1 (includes day of surgery)
	Patient	
Jan 1, 2013 to Dec 1, 2018 (to account for prolonged LOS postop from the end of inclusion date)
	
Part of inclusion criteria: if a patient had multiple surgeries, the first surgery with a LOS >1 (i.e. at least overnight stay). To calculate ratio of LOS to Expected Length of Stay (ELOS) as secondary outcome. We have chosen to standardize LOS to only include duration of stay after surgery, since there are many factors that may prolong a patient's stay prior to surgery.

Additional Demographic Information				
CIHI DAD	SEX: Patient sex	Patient	
Jan 1, 2013 to Dec 1, 2017
	
As sex may affect outcomes, this will be included as a covariate in our models
 
M = Male
 
F = Female

HSM	BMI: Body Mass Index [Derived by Innovian]	Patient	
Jan 1, 2010 to Dec 1, 2017
	
Dichotomized according to WHO definition for obesity: BMI>30. This will be combined with ICD code to create a binary Obesity variable (please see below).

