CIHI-DAD	Admit-date	Patient	1Jan2010 to 31Dec2017	
For 3-year look-back window with: either admission date or discharge date is between surgery date (B) and 3 years before B (A), assuming that A<B.
 
For 30-day follow-up window with: Either admission date or discharge date is between surgery date (B) and 30 days after B (C), assuming that B<C.

CIHI-DAD	Discharge_date	Patient	1Jan2010 to 31Dec2017	For 3-year look-back window with: either admission date or discharge date is between surgery date (B) and 3 years before B (A), assuming that A<B.

				For 30-day follow-up window with: Either admission date or discharge date is between surgery date (B) and 30 days after B (C), assuming that B<C.
CIHI DAD	ECI: Elixhauser comorbidity index [Derived by HDNS]	Patient	Jan 1, 2010 to Dec 1, 2017 (3 years before and including date of surgery)	
To be computed by the HDNS according to protocol (32) using DXCODES (please see above), to be included into model as covariate. Please report both total score, and any of the following individual categories:
 
Congestive heart failure Cardiac arrhythmias Valvular disease Pulmonary circulation disorders Peripheral vascular disorders Hypertension, uncomplicated Hypertension, complicated Paralysis Other neurological disorders Chronic pulmonary disease Diabetes, uncomplicated Diabetes, complicated Hypothyroidism Renal failure Liver disease Peptic Ulcer Disease Excluding Bleeding AIDS/HIV Lymphoma Metastatic cancer Solid tumor without metastasis Rheumatoid arthritis/ collagen vascular diseases Coagulopathy Obesity Weight loss Fluid and electrolyte disorders Blood loss anemia Deficiency anemia Alcohol abuse Drug abuse Psychoses

				Depression

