CIHI DAD	
ICU admission [Derived by HDNS]
 
SCUNUM[1-n]: Special Care Unit Num “The SCU Unit Number is a code identifying the type of special care unit where the patient receives critical care.”
 
[Derived by HDNS]
	Patient	
Jan 1, 2013 to Dec 31, 2017
	
Two variables to be derived:
 
 1. Preoperative ICU (yes/no) 2. Postoperative ICU (yes/no) 
Preoperative ICU admission (yes/no) is a covariate to be included into the model. Postoperative ICU admission (yes/no) is a secondary outcome to be included into model. Descriptive statistics will be performed.
 
Derivation process: ICU = yes include the following SCUNUM: 10 = Medical Intensive Care Nursing Unit 20 = Surgical Intensive Care Nursing Unit 25 = Trauma Intensive Care Nursing Unit 30 = Combined Medical/Surgical Intensive Care Nursing Unit 35 = Burn Intensive Care Nursing Unit 40 = Cardiac Intensive Care Nursing Unit Surgery 45 = Coronary Intensive Care Nursing Unit 80 = Respirology Intensive Care Nursing Unit Else ICU = no
 
If the SCU Admit Date is on or before PDATE, then it would be defined as Preoperative AND postoperative ICU admission. Else, postoperative ICU admission only.

CIHI DAD	READMIT: Readmission Code (within 30 days after PDATE) [Derived by HDNS]	Patient	Jan 1, 2013 to Dec 31, 2017	
Readmission within 30 days of PDATE (yes/no) is a secondary outcome to be included into model. Descriptive statistics will be performed.
 
Derived: Postoperative readmission = yes include the following:
 
 1 = Planned readmission from previous acute care 2 = Unplanned readmission within 7 days following discharge from acute care 3 = Unplanned readmission 8 – 28 days following discharge from acute care 4 = ≤ 7 days, unplanned 5 = New patient 9 = None of the above. 
Else Postoperative readmission = no

CIHI DAD	LOS:EOS Ratio of Length of Stay (LOS) to Expected Length of Stay (EOS) as assigned by the Case Mix Grouping [Derived by HDNS]	Patient	Jan 1, 2013 to Dec 31, 2017	
This will be dichotomized by HDNS: LOS:EOS > 1 (yes/no). This is a secondary outcome to be included into model. Descriptive statistics will be performed.

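### Readmission is scored yes/no from the surgery date for every patient, so those who die in the surgical stay or leave late have little or no time at risk and are grouped with patients who went home and stayed out

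*Combined protocol and SAP*

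**What the plan says.** The outcome list in the protocol body (Outcomes, Secondary, item 4) gives only "Hospital readmission within 30 days (yes/no", with no starting point. The READMIT row of Appendix 1 supplies it: the variable is "READMIT: Readmission Code (within 30 days after PDATE", and "Readmission within 30 days of PDATE (yes/no) is a secondary outcome to be included into model". The row then lists the codes that count as yes and closes with "Else Postoperative readmission = no".

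Other parts of the plan bear on this:

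- The PDATE row limits follow-up: "for all other variables we only need data within 30 days after PDATE".
- The admission and discharge date rows use the same window: "Either admission date or discharge date is between surgery date (B) and 30 days after B (C), assuming that B<C".
- LOS is "discharge date minus PDATE + 1 (includes day of surgery".
- In-hospital death is derived, but for descriptive statistics among those who died within 30 days, not to define who can be readmitted.
- Under Evaluating model performance, the best primary-outcome model is reused for the secondary outcomes. No method for unequal time at risk or competing death is named.
- Days alive and out of hospital at 30 days is a separate secondary outcome (item 6).

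**The concern.** A patient can be readmitted only after leaving hospital alive. Under the rule as written, three different histories end in the same category: discharged and not readmitted, died during the surgical stay, and still in hospital on day 30. Only the first is a good result for this outcome. Among patients who are discharged, each extra postoperative day in hospital removes one day in which a readmission could be recorded.

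This matters because the plan will report associations between hemodynamic thresholds and the secondary outcomes. It hypothesises that the exposures are associated with 30-day death and major in-hospital morbidity, and it studies prolonged stay as an outcome. An exposure that goes with early death or longer stay also goes with less time at risk, so its association with readmission is understated and could appear protective. A readmission model built this way would tend to rate long-stay patients as low risk, against the stated aim of finding high-risk patients for closer follow-up.

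**Working it through.** **The plan's own figure.** No readmission rate or sizing is given. The only sizing figure concerns mortality: 24,000 × 0.017 = 408 deaths in the derivation group, which reproduces. Applied to the whole cohort, 35,000 × 0.017 = 595. The 1.7% is an in-hospital rate after major surgery that the plan borrows for its 30-day outcome. The 595 is therefore an approximate scale for in-hospital deaths, not a bound.

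**Days at risk.** Since LOS = discharge date − PDATE + 1, discharge falls on day LOS − 1. Days left in the window = max(0, 30 − (LOS − 1)) = max(0, 31 − LOS).

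| LOS | Days at risk |
|---|---|
| 2 | 29 |
| 4 | 27 |
| 5 | 26 |
| 7 | 24 |
| 20 | 11 |
| 28 | 3 |
| 31 or more | 0 |
| Died in the surgical stay | 0 |

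**Effect on the odds ratio, equal hazard.** Assume a constant daily hazard h after discharge, the same in both groups. This is an assumption; the documents give no rate. Recorded risk P = 1 − (1 − h)^(31 − LOS). At h = 0.004:

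- LOS 2: 1 − 0.996^29 = 11.0%
- LOS 4: 1 − 0.996^27 = 10.3%
- LOS 5: 1 − 0.996^26 = 9.9%
- LOS 7: 1 − 0.996^24 = 9.2%
- LOS 20: 1 − 0.996^11 = 4.3%
- LOS 28: 1 − 0.996^3 = 1.2%

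The true ratio of hazards is 1. The odds ratios that result are:

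| Contrast | h = 0.002 | h = 0.004 | h = 0.006 |
|---|---|---|---|
| LOS 7 against 5 | 0.92 | 0.92 | 0.92 |
| LOS 7 against 4 | 0.89 | 0.88 | 0.88 |
| LOS 20 against 2 | 0.37 | 0.37 | 0.36 |

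The baseline hazard hardly matters; the difference in stay drives the result.

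**Effect when the longer-stay group truly has the higher hazard** (reference group h = 0.004):

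- LOS 7 against 4, hazard doubled: P = 17.5% against 10.3%, odds ratio 1.86. With 27 days at risk in both groups it would be 2.12. This is attenuation, not reversal.
- LOS 20 against 2, hazard doubled: P = 8.5% against 11.0%, odds ratio 0.75. With 29 days in both groups it would be 2.13. This is reversal.
- LOS 20 against 2, hazard tripled: P = 12.4% against 11.0%, odds ratio 1.15. With 29 days in both groups it would be 3.40. This is strong attenuation, with the sign kept.

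**Adding in-hospital death.** Suppose the comparison group leaves on day 3 with no deaths, and the sicker group leaves on day 10, 15 or 20 with 5% dying in hospital. Across 30-day post-discharge risks of 5% to 15% with equal hazard, the surgery-date definition gives odds ratios of about 0.69–0.70, 0.51–0.52 and 0.33–0.35. With a true doubling of the hazard it gives 1.42–1.44, 1.06 and 0.69–0.70. A full 30 days from discharge among those discharged alive gives 1.00 and 2.05–2.18 respectively.

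**The case against.** The strongest reply is that a fixed window from surgery is a legitimate definition. It matches the plan's other 30-day outcomes and the data window requested, and it answers a clear question: was the patient back in hospital by day 30? That stands. A reader might infer that anchoring on PDATE is itself an error; the documents do not support that. The gap is the missing at-risk set and the missing rule for death and continued stay.

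Four other stronger readings also go too far:

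- **That the sign will reverse.** The 0.37 compares two extreme LOS groups, not exposure groups, and assumes equal hazards. Modest LOS differences give 0.88 to 0.92, and a real excess hazard can keep the ratio above 1.
- **That the plan certainly scores deaths as 'no'.** This holds if the variable is read from a later admission record. The yes list also contains code 5 (new patient) and code 9 (none of the above), and the date window can catch the surgical record through its discharge date. Read from that record, such patients could score 'yes'. The code list needs its own reconciliation.
- **That the codes and the window contradict each other.** Codes such as "2 = Unplanned readmission within 7 days following discharge from acute care" count from discharge, but they can describe the type of readmission while PDATE + 30 acts as a date filter. Both can apply, though the row should say so.
- **That the plan hypothesises longer stay.** Its hypotheses name mortality and major in-hospital morbidity. Prolonged stay is an outcome under study.

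Mortality, prolonged stay, and days alive and out of hospital are reported alongside, so death and long stay remain visible. They do not repair the readmission variable.

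**Conclusion.** The concern holds for one secondary outcome and should be corrected before the variable is derived. As written, time at risk is 31 − LOS days for patients discharged alive within the window and zero for those who die in the surgical stay or remain in hospital on day 30. No rule separates these patients from those discharged and not readmitted. Associations for exposures linked to early death or longer stay are pulled toward or below the null.

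The size cannot be fixed from the documents. Under a constant, equal hazard of 0.4% a day it runs from a mild 0.88–0.92 (LOS 7 against 4 or 5) to 0.37 (LOS 20 against 2). Reversal needs large differences in stay and is possible, not certain. The direction rests on the variable being read from a later admission record. The primary outcome is unaffected.

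**What to change.** Specify in the outcome list and the READMIT row:

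1. **At-risk set:** patients discharged alive from the surgical stay within the window. Report the numbers who died in that stay or were still in hospital on day 30 separately.
2. **Analysis:** time from discharge to first readmission, censored at day 30 after PDATE and no later than December 31, 2017, with death after discharge as a competing event.
3. **All-patient statements:** use days alive and out of hospital (secondary outcome 6).
4. **Code list:** say which record READMIT is read from and reconcile the codes, including 5 and 9, as a separate correction.

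Admission, discharge and death dates within PDATE + 30 are already requested. Date of death is for internal use by the data custodian, so the custodian should derive the event times. The cost is specification wording, one derivation and a time-to-event model in place of the reused binary one. The denominator is slightly smaller and the result is conditional on live discharge. Because stay length sets the censoring time, information late after discharge comes mainly from short-stay patients, which should be stated.

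A full 30-day clock from discharge is optional. It would mean widening the follow-up window in the PDATE and admission/discharge date rows: a discharge on day 19 needs records to day 49. Late entries should then be censored at December 31, 2017. A discharge-date cutoff would selectively drop long stays among late-2017 surgeries, all of them in the validation group.

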Appendix 1. Summary of Variables

Source Dataset	Variable	Level of Identification	Time Span	Why is this element required in the analysis?
Information for inclusion and data linkage				
Innovian	Date of surgery	Patient	Jan 1, 2013 to Dec 1, 2017	
Part of HDNS data linkage with Innovian to ensure only variables from the surgical admission of interest (first surgery admission with LOS>1) is included. This Date of Surgery will be used to confirm linkage with “PDATE” from CIHI DAD to ensure that data from the correct surgical admission is included. The maximum allowable mismatch for the surgery dates in Innovian and CIHI is +/- 1 day. The Innovian surgery date will be used as the gold standard, since the record is done in real time and thus the most accurate.
 
The date of surgery will also be used to divide the cohort temporally into the derivation/training group (January 1, 2013 – November 30, 2016), and validation group (December 1, 2016 – December 1, 2017)

Innovian	Patient_ID: encrypted health card number	Patient	Jan 1, 2013 to Dec 1, 2017	HDNS data linkage with Innovian. The dataset given to us will not contain Patient_ID, but rather a Study ID.
Innovian	Age: on date of surgery	Patient	Jan 1, 2013 to Dec 1, 2017	Age ≥ 45 part of inclusion criteria. Also, as age may impact outcomes, this will be included as a covariate in our models
Innovian	Organ donation: Procedure name	Patient	Jan 1, 2013 to Dec 1, 2017	Patients with procedure name that includes “organ donor” or “organ donation” will be excluded, since they are already declared brain dead and

	containing the word “Organ donor” or “Organ donation” or “DCD” [Derived by Innovian]			will not reflect the usual surgical population.
Innovian	Cardiac surgery [Derived by Innovian]	Patient	Jan 1, 2013 to Dec 1, 2017	As defined by ProcedureAnatomy = “heart” or “cardiac”. Cardiac surgery patients are excluded since they are receiving surgery directly on the heart and have a unique set of complications that may not reflect the usual surgical population.
Innovian	ASA: American Society of Anesthesiologist class (I to VI)	Patient	Jan 1, 2013 to Dec 1, 2017	Patients with ASA VI (i.e. patient with neurologic brain death for organ donation) will be excluded. Also, as this may affect outcomes, it will be included as a covariate in our models.

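### The READMIT row counts every printed code as a readmission and names no source record, so index surgical stays could be counted as readmissions

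*Combined protocol and SAP*

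**What the plan says.** The Outcomes section lists hospital readmission within 30 days, yes or no, as secondary outcome 4. The derivation is in Appendix 1, in the READMIT row, which is marked as derived by HDNS. Its title sets a limit of 30 days after the procedure date (PDATE), and it states: "Readmission within 30 days of PDATE (yes/no) is a secondary outcome to be included into model".

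The coding rule opens with "Derived: Postoperative readmission = yes include the following". Six codes follow:
- code 1, planned readmission;
- codes 2 and 3, unplanned readmission up to 7 days and at 8 to 28 days after acute-care discharge;
- code 4, unplanned within 7 days;
- code 5, new patient;
- "9 = None of the above".

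The rule closes with "Else Postoperative readmission = no".

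Other Appendix 1 rows bear on which record is read:
- The Date of surgery row describes the linkage as a step "to ensure only variables from the surgical admission of interest (first surgery admission with LOS>1) is included".
- The PDATE row says the same in the words "to ensure that only the admission corresponding to the surgery admission of interest (first surgery admission with LOS>1) is included". It then notes that, comorbidity data aside, "for all other variables we only need data within 30 days after PDATE".
- The Admit-date and Discharge_date rows set a 30-day follow-up window. A stay qualifies if either its admission date or its discharge date lies between surgery and day 30.
- The ICU admission row, directly above READMIT, uses the same list-then-else layout but adds a timing rule: "If the SCU Admit Date is on or before PDATE, then it would be defined as Preoperative AND postoperative ICU admission". The READMIT row has no equivalent.

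**The concern.** A derivation rule should sort patients into two groups. Here every printed code leads to yes. By their labels, codes 5 and 9 do not describe a return to hospital. The rule can therefore work only if something else restricts the records to which it is applied, namely that only admissions after the index discharge are read. The row hints at this but does not say it.

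This matters because a third party builds the variable from the row. If index surgical records are among those read, any patient whose index record carries a listed code is recorded as readmitted, and the variable no longer measures return to hospital. The same flag would then enter the secondary-outcome modelling described under Evaluating model performance. It would also enter the first principal component model, which takes in all outcomes.

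**Working it through.** The plan gives no rate, sample size or power for readmission, so there is no figure to reproduce. The check enumerates the rule and sets the index stay's dates against the follow-up window.

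**1. The code list (READMIT row).** Printed codes: {1, 2, 3, 4, 5, 9}. Codes mapped to yes: {1, 2, 3, 4, 5, 9}. Printed codes left for the else branch: none. So 6 of 6 give yes. Only a value that is not printed, such as a blank, could give no. Moving codes 5 and 9 to no would leave 4 of 6 as yes.

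**2. Can the index stay fall inside the follow-up window?** The LOS row gives LOS = discharge date − PDATE + 1, and inclusion requires LOS > 1. Hence discharge date = PDATE + LOS − 1.
- Shortest eligible stay: LOS 2, discharge on PDATE + 1.
- Last stay inside by discharge date, counting day 30: LOS − 1 = 30, so LOS 31.
- So every index stay with LOS 2 to 31 qualifies through its own discharge date, whenever the patient was admitted.
- If the day of surgery also counts, an index stay admitted that day qualifies at any LOS.
- Index stays outside the window are those admitted before PDATE with LOS of 32 or more. Those patients are still in hospital at PDATE + 30.

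**3. Consequences by reading.**

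| Records to which the list is applied | Result |
|---|---|
| All records in the 30-day window | Index stays carrying a listed code are counted as readmissions |
| Index record only | The same, and true later returns are not seen |
| Later admissions only | Any later record with a listed code is yes; the list is redundant and transfers are not screened out |

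**4. Would deleting codes 5 and 9 be enough?** No. Codes 2 and 3 count days from acute-care discharge, while the outcome counts from PDATE.
- LOS 2: code 3 reaches PDATE + 1 + 28 = PDATE + 29, one day short of the outcome window.
- LOS 3: it reaches PDATE + 2 + 28 = PDATE + 30.
- LOS 8: it reaches PDATE + 7 + 28 = PDATE + 35, beyond the window.

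The codes therefore do not match the outcome window, and deleting two of them still would not name the record to be read.

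**5. Are the dates available for a date rule?** Admission and discharge dates are requested to 31 December 2017. The last eligible surgery date is 1 December 2017, and 1 December + 30 days = 31 December. PDATE + 30 is covered for every eligible patient.

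**The case against.** The strongest reply is that the row already excludes the index stay by implication. It concerns readmission, limits it to 30 days after PDATE and calls the variable postoperative. An index admission contains PDATE and so began on or before it. If the limit applies to the admission date, the index stay drops out, except perhaps where admission and surgery fall on the same day. Every later stay then counts whatever its code, which is ordinary all-cause readmission and fits the Outcomes section. This is the most natural reading, and under it the outcome is largely usable. What it lacks is any sentence saying that the limit applies to the admission date, or that the index record is left out.

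Two stronger readings are tempting, and the documents do not support them.
- A reader might infer from the linkage wording in the Date of surgery and PDATE rows that only the index record is ever read. That wording serves to match surgical admissions. Taken literally, it would defeat the three-year look-back and the 30-day follow-up window that the same Appendix requires.
- A reader might infer that nearly every patient would be coded as readmitted. That needs index records to be read and most of them to carry a listed code. No section shows how index records are coded.

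It is also fair to say that the labels of codes 5 and 9 do not settle how the field is assigned on a later record, since the documents include no data dictionary. The planned descriptive statistics would probably expose a gross error before modelling. That limits the harm but leaves the rule as it stands.

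**Conclusion.** The rule is defective as written: the code list does not discriminate, and nothing explicit keeps the index stay out. The only operational follow-up window in the plan lets index stays with LOS 2 to 31 in through their discharge date. Whether this does harm depends on how HDNS applies the row. Applied to all records in the window, index stays with a listed code are miscounted as readmissions. Applied to later admissions only, the list is superfluous and the remaining weakness is that transfers are not screened out.

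The effect is confined to secondary outcome 4, one of six numbered secondary outcomes, and to the analyses that use it. The 30-day mortality outcome comes from Vital Statistics and is unaffected. The size of the error cannot be computed, because the documents give no readmission rate, length-of-stay distribution or code frequencies. The LOS 2 to 31 result assumes that day 30 is counted. Severity is minor to should-fix, with moderate confidence.

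**What to change.** Replace the code list in the READMIT row with a date rule. Readmission is yes if there is a DAD admission record that meets all of these conditions:
- it is not the index record;
- it is not a direct transfer continuing the index episode;
- its admission date is on or after the index discharge date;
- its admission date is no later than PDATE + 30.

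Otherwise readmission is no. Codes 5 and 9 should not serve as criteria for yes. The row should also say that the index-admission linkage wording in the Date of surgery and PDATE rows does not restrict this variable.

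The cost is one reworded row, made before HDNS runs the derivation. The dates needed are already requested. The drawback is that HDNS must tell same-day transfers from same-day returns. The institution-from field already requested for the emergency-surgery flag may help, but the documents do not show that it is sufficient.
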